4.10.4. Laboratory Measures

The data from laboratory testing will be summarized by treatment and visit. Change from baseline (last nonmissing value up to Visit 3) to postbaseline value for laboratory tests (except for FSG, HbA1c, and Antibody) will be summarized for patients who have both a baseline and at least 1 postbaseline result. Treatment differences in mean change for these laboratory tests will be evaluated using MMRM model. The MMRM model will be used for the analysis during the treatment period and will contain the term for treatment, baseline value, visit, and visit-by-treatment interaction as factors, patient as random effect, and compound symmetric as the variance-covariance structure. Analyses will be provided in both international units (SI) and conventional units (CN). The MMRM analysis will only include lab tests for the scheduled visits specified in the protocol. For selected lab measures, log-transformed value will be used in MMRM, and the geometric LS means as well as the percentage change from baseline will be reported.

The percentages of patients with treatment-emergent abnormal laboratory results at any time after randomization (including the treatment period and follow-up period) will be summarized and compared between treatment groups using Fisher's exact test. A treatment-emergent abnormal result is defined as a change from normal at baseline to abnormal at any time after randomization. Covance reference ranges will generally be used to define the low and high limits. Patients with missing baseline lab measures will be excluded from this analysis unless otherwise specified. Scheduled visits, unscheduled visits, and retest measurements will be included in this analysis.

A lab listing of patients in the safety population who had an abnormal laboratory value during the study will be provided, including the actual measurement (in both SI and CN unit), abnormal result, and reference low or high limits.

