4.1. General Considerations

All data will be entered, verified, and archived at a contract research organization (CRO) external to Eli Lilly and Company (Lilly) and/or at Lilly. Data listings, summaries, and analyses will be performed by a CRO and/or by Lilly under the guidance and approval of statisticians at Lilly.

Statistical analysis of this study will be the responsibility of Lilly. Any change to the data analysis methods described in the protocol will require an amendment ONLY if it changes a principal feature of the protocol. Any other change to the data analysis methods described in the protocol, and the justification for making the change, will be described in this SAP and/or in the clinical study report (CSR). Additional exploratory analyses will be conducted, as deemed appropriate.

Unless otherwise specified, listings will be ordered by the patient ID nested within the investigator site.

The patient populations used for this study are described below:

Population and Analysis Set	Description
Entered/Enrolled Population	All study participants who sign informed consent
Randomized Population	All study participants who are randomly assigned a treatment arm
Efficacy analysis set (EAS)	Data for all randomized study participants who receive at least one dose of study medication, excluding data after using rescue medication(not acute therapy) or stopping study medication (last dose date + 10 days). In the event of a treatment error, participants will be analyzed according to the treatment they actually received.
Safety Population	All randomized study participants who receive at least one dose of study medication.
CGM Population	All randomized study participants who receive at least 1 dose of study medication, and have CGM data from at least 1 collection period.

Abbreviations: CGM = continuous glucose monitoring.

Safety analyses will be conducted using the Safety Population with all data collected during the study including treatment and follow-up period regardless of the treatment disposition status. Efficacy analyses will be conducted on the efficacy analysis set (EAS), unless otherwise specified.

Unless otherwise noted, all tests of treatment effects will be conducted at a 2-sided alpha level of 0.10 and confidence intervals (CIs) will be calculated at 90%, 2-sided. All tests of interactions between treatment groups and other factors will be conducted at a 2-sided alpha level of 0.10.

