4.10.5. Vital Signs and Body Weight

Vital signs and weight will be summarized by treatment and visit. Change from baseline (last nonmissing value up to Visit 3) to postbaseline value for vital signs and weight will be summarized for patients who have both a baseline and at least 1 postbaseline result.

Treatment differences in mean change will be assessed using MMRM. The MMRM model will be used for the analysis during the treatment period and will contain the terms for treatment, baseline value, visit, and visit-by-treatment interaction as factors; patient as random effect; and CS as the variance-covariance structure. Only scheduled measures will be included in the MMRM analyses.

The percentages of patients with treatment-emergent high or low vital signs at any time after randomization will be summarized and compared between treatment groups using Fisher's exact test. A treatment-emergent high result is defined as a change from a value less than or equal to the high limit (140 mm Hg for systolic blood pressure, 90 mm Hg for diastolic blood pressure, and 100 bpm for pulse) at baseline to a value greater than the high limit at any time that meets the specified change criteria after randomization. A treatment-emergent low result is defined as a change from a value greater than or equal to the low limit (90 mm Hg for systolic blood pressure, 50 mm Hg for diastolic blood pressure, and 50 bpm for pulse) at baseline to a value less than the low limit at any time that meets the specified change criteria after randomization. Patients with missing baseline measures will be excluded from this analysis unless otherwise specified. Scheduled visits, unscheduled visits, and retest measurements will be included in this analysis. [Table BDCM.3](#) will be used to define the low and high limits and change thresholds.

Table BDCM.3. Categorical Criteria for Abnormal Treatment-Emergent Blood Pressure and Pulse Measurement

Parameter	Low	High
Systolic BP (mm Hg) (Supine or sitting)	≤ 90 and decrease from baseline ≥ 20	≥ 140 and increase from baseline ≥ 20
Diastolic BP (mm Hg) (Supine or sitting)	≤ 50 and decrease from baseline ≥ 10	≥ 90 and increase from baseline ≥ 10
Pulse (bpm) (Supine or sitting)	< 50 and decrease from baseline ≥ 15	> 100 and increase from baseline ≥ 15

Abbreviations: BP = blood pressure; bpm = beats per minute.

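### The treatment-emergent laboratory rule has no direction, and neither it nor the vital-signs rule states an at-risk denominator, so some shifts go uncounted and percentages are diluted

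*SAP*

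**What the plan says.** **Laboratory tests (SAP 4.10.4).** The event is a single category: "A treatment-emergent abnormal result is defined as a change from normal at baseline to abnormal at any time after randomization". The section acknowledges two limits ("Covance reference ranges will generally be used to define the low and high limits") but defines no separate treatment-emergent low and high. On who is left out, it says only: "Patients with missing baseline lab measures will be excluded from this analysis unless otherwise specified". The condition "will be summarized for patients who have both a baseline and at least 1 postbaseline result" belongs to the change-from-baseline summary, not to this categorical analysis. Percentages are compared between arms by Fisher's exact test, and under SAP 4.1 "all tests of treatment effects will be conducted at a 2-sided alpha level of 0.10".

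**Vital signs (SAP 4.10.5).** This rule has direction. For low results: "A treatment-emergent low result is defined as a change from a value greater than or equal to the low limit", to a value below it. The high rule mirrors this, and both also require the change thresholds in SAP Table BDCM.3. The stated exclusion is again only a missing baseline: "Patients with missing baseline measures will be excluded from this analysis unless otherwise specified".

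**The concern.** There are two separate problems.

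- **Direction.** The laboratory rule requires a normal baseline. A participant outside the range on one side at baseline who ends up outside it on the other side has a new abnormality, but the rule cannot count it. One SAP thus applies two different rules to the same idea.
- **Denominator.** A participant already abnormal at baseline cannot meet the laboratory definition, and one already above the high limit cannot become treatment-emergent high under the vital-signs definition. If such participants stay in the percentage, they count as event-free. The reported figure then depends on how many people started abnormal as well as on what happened during treatment.

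At stake are the accuracy of these safety percentages and, if baseline abnormality differs by arm, the Fisher comparison built on them.

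**Working it through.** The documents state no figure for this point, so there is nothing to reproduce. The check is a comparison of the two rules, then arithmetic on the denominator.

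**1. Direction**

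| Baseline | Later value | Rule in 4.10.4 | Directional rule as in 4.10.5 |
|---|---|---|---|
| Within range | Above | Counted | Counted (high) |
| Within range | Below | Counted | Counted (low) |
| Above range | Below | Not counted | Counted (low) |
| Below range | Above | Not counted | Counted (high) |

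The last column leaves aside the extra change thresholds that apply to vital signs. The third and fourth rows are the loss.

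**2. Dilution of the percentage**

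Let f be the share abnormal at baseline and r the risk among those at risk. With everyone who has a baseline in the denominator, reported % = r × (1 − f). The value of f is an assumption. For r = 20%:

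- f = 5%: 20 × 0.95 = 19%
- f = 10%: 20 × 0.90 = 18%
- f = 20%: 20 × 0.80 = 16%
- f = 30%: 20 × 0.70 = 14%
- f = 40%: 20 × 0.60 = 12%

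**3. Effect on the comparison when f is equal across arms**

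Inputs: 125 participants per arm (Protocol Synopsis), two-sided Fisher test at 0.10 (SAP 4.1), and assumed at-risk risks of 30% and 15%. Exact enumeration gives:

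| f in both arms | Power, all participants | Power, at-risk only |
|---|---|---|
| 20% (100 at risk per arm) | 76.5% | 77.9% |
| 40% (75 at risk per arm) | 61.4% | 65.2% |

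**4. Effect on the comparison when f differs**

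Take f = 12% in one arm and 28% in the other, so 110 and 90 of 125 are at risk.

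- With an equal true risk of 20%, the literal rule expects 0.20 × 110/125 = 17.6% against 0.20 × 90/125 = 14.4%.
- With an equal true risk of 30%, the Fisher test rejects 17.7% of the time using all participants and 8.6% using those at risk, against a nominal 10%.

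How likely is that imbalance? The average f is 20%, so the standard error of the difference is √(0.20 × 0.80 × 2/125) = 0.0506. The gap of 0.16 is 0.16/0.0506 = 3.2 standard errors.

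**The case against.** **The denominator is inferred.** The SAP never writes it out. A programmer could read the requirement of a normal baseline as restricting the denominator too. This stands. The dilution follows from the literal text, under which a missing baseline is the only exclusion, and the ambiguity is itself a reason to state the rule.

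**Randomization protects the comparison.** This largely stands. With similar f in each arm both percentages shrink alike and little power is lost. The 17.7% rejection rate needs an imbalance that is improbable for any given analyte.

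**Other outputs cover the gap.** This stands in part. The listing in SAP 4.10.4 shows participants with abnormal values together with the limits. Protocol 10.3.4.4 compares maximum and minimum postbaseline values with baseline against the reference ranges, although SAP 4.10.4 does not restate this. SAP 4.10.4.2 tabulates ALT, AST and total bilirubin elevations by baseline category. None of these corrects the treatment-emergent percentages or their test.

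**A stronger reading about glucose.** A reader might infer that, in an insulin trial, the rule hides most new low glucose values because most participants start high. The documents do not support that. SAP 4.10.3.2 analyses hypoglycemia rate and incidence at <54 and ≤70 mg/dL, and SAP 4.11.2.1 adds CGM time below range and episodes; neither requires a normal baseline. The share starting above range is not given either. If 85% to 95% started high and all were equally likely to go low, the rule would miss 85% to 95% of new lows. If those with a normal baseline were three times as likely to go low, it would miss 0.85/(0.85 + 3 × 0.15) = 65% to 0.95/(0.95 + 3 × 0.05) = 86%. With 70% high it would miss 0.70/(0.70 + 3 × 0.30) = 44%. These are assumptions about one line of one table and do not measure a lost hypoglycemia signal.

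**Conclusion.** The concern holds, within limits. On direction, the wording of SAP 4.10.4 gives a wrong count for any shift from one side of the range to the other, and SAP 4.10.5 shows that the SAP already has the right form. How many such shifts would occur cannot be said from the documents.

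On the denominator, the literal text of both sections scales the percentage by (1 − f). This matters for the reported incidence, and for the between-arm comparison only if f differs between arms.

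The consequence is confined to these treatment-emergent tables. Clinical laboratory results are an exploratory endpoint in Protocol Table BDCM.2 and SAP 3.3, and the primary analysis is untouched. A reader might also infer that the Fisher tests are generally invalid. The working does not show that: the inflation arises only under a marked baseline imbalance.

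**What to change.** - **In SAP 4.10.4**, define two events per test. Treatment-emergent high is a baseline at or below the upper limit with a later value above it. Treatment-emergent low is a baseline at or above the lower limit with a later value below it.
- **In SAP 4.10.4 and 4.10.5**, base each percentage and Fisher test on participants who were not already abnormal in that direction at baseline and who have at least one postbaseline result. Show the number at risk by arm.

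The cost is a wording change and routine programming. Denominators become somewhat smaller and will differ between tests and directions, which is why the number at risk should be displayed. No new data are required.

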4.10.4.1. Lipid Measures

Triglycerides, total cholesterol, LDL-C, and HDL-C (results from fasting samples) will take log-transformation before being analyzed by MMRM model define above for the Safety population.

A listing of patients with postbaseline fasting triglyceride value ≥ 400 mg/dL or non-fasting triglycerides > 600 will be provided (scheduled visits, unscheduled visits, and repeat measurements will be included).

4.10.4.2. Liver Enzyme Elevation Measures

The liver enzymes and biomarkers (alanine aminotransferase [ALT], aspartate aminotransferase [AST], Alkaline phosphatase [ALP], total bilirubin[TBL], and Gamma glutamyl transferase [GGT]) measures will take log-transformation before performing the MMRM analysis. In addition, the percentage of patients with the following elevations in liver enzymes at any postbaseline visit after randomization including the treatment period and post-treatment follow-up period will be summarized for subsest based on baseline categories.

- The analysis of any postbaseline ALT (AST) ≥ 3 fold (3X) ULN will contain 4 baseline subsets:
 - patients whose non-missing maximum baseline value is less than or equal to 1X ULN,
 - patients whose maximum baseline is greater than 1X ULN but less than 3X ULN,
 - patients whose maximum baseline value is greater than or equal 3X ULN, and
 - patients whose baseline values are missing.
- The analysis of any postbaseline ALT (AST) ≥ 5 X ULN will be contain 5 baseline subsets:
 - patients whose non-missing maximum baseline value is less than or equal to 1X ULN,
 - patients whose maximum baseline is greater than 1X ULN but less than 3X ULN,
 - patients whose maximum baseline is greater than or equal to 3X ULN but less than 5X ULN,
 - patients whose maximum baseline value is greater than or equal to 5X ULN, and
 - patients whose baseline values are missing.
- The analysis of any postbaseline ALT(AST) ≥ 10 X ULN will contain 6 baseline subsets:

- patients whose non-missing maximum baseline value is less than or equal to 1X ULN,
 - patients whose maximum baseline is greater than 1X ULN but less than 3X ULN,
 - patients whose maximum baseline is greater than or equal to 3X ULN but less than 5X ULN,
 - patients whose maximum baseline is greater than or equal to 5X ULN but less than 10X ULN,
 - patients whose maximum baseline value is greater than or equal to 10X ULN, and
 - patients whose baseline values are missing.
- The analysis of any postbaseline TBL $\geq 2X$ ULN will contain 4 baseline subsets:
 - patients whose non-missing maximum baseline value is less than or equal to 1X ULN,
 - patients whose maximum baseline is greater than 1X ULN but less than 2X ULN,
 - patients whose maximum baseline value is greater than or equal to 2X ULN, and
 - patients whose baseline values are missing.

A listing of patients with any post randomization

- elevation of serum ALT to ≥ 3 -fold ULN on 2 or more consecutive blood tests
- elevation of serum ALT to ≥ 5 -fold ULN on 2 or more consecutive blood tests
- elevation of serum AST to ≥ 3 -fold ULN / 5-fold ULN on 2 or more consecutive blood tests
- elevated serum TBL to ≥ 2 -fold ULN (except for cases of known Gilbert's syndrome)
- elevation of serum ALP to ≥ 2 -fold ULN on 2 or more consecutive blood tests
- study participant discontinued from treatment due to a hepatic event or abnormality of liver tests
- hepatic event considered to be an SAE

will be provided, including the actual measurement of ALT, AST, TBL, ALP, and the corresponding reference of high limits.

4.10.5. Vital Signs and Body Weight

Vital signs and weight will be summarized by treatment and visit. Change from baseline (last nonmissing value up to Visit 3) to postbaseline value for vital signs and weight will be summarized for patients who have both a baseline and at least 1 postbaseline result.

Treatment differences in mean change will be assessed using MMRM. The MMRM model will be used for the analysis during the treatment period and will contain the terms for treatment, baseline value, visit, and visit-by-treatment interaction as factors; patient as random effect; and CS as the variance-covariance structure. Only scheduled measures will be included in the MMRM analyses.

The percentages of patients with treatment-emergent high or low vital signs at any time after randomization will be summarized and compared between treatment groups using Fisher's exact test. A treatment-emergent high result is defined as a change from a value less than or equal to the high limit (140 mm Hg for systolic blood pressure, 90 mm Hg for diastolic blood pressure, and 100 bpm for pulse) at baseline to a value greater than the high limit at any time that meets the specified change criteria after randomization. A treatment-emergent low result is defined as a change from a value greater than or equal to the low limit (90 mm Hg for systolic blood pressure, 50 mm Hg for diastolic blood pressure, and 50 bpm for pulse) at baseline to a value less than the low limit at any time that meets the specified change criteria after randomization. Patients with missing baseline measures will be excluded from this analysis unless otherwise specified. Scheduled visits, unscheduled visits, and retest measurements will be included in this analysis. [Table BDCM.3](#) will be used to define the low and high limits and change thresholds.

Table BDCM.3. Categorical Criteria for Abnormal Treatment-Emergent Blood Pressure and Pulse Measurement

Parameter	Low	High
Systolic BP (mm Hg) (Supine or sitting)	≤ 90 and decrease from baseline ≥ 20	≥ 140 and increase from baseline ≥ 20
Diastolic BP (mm Hg) (Supine or sitting)	≤ 50 and decrease from baseline ≥ 10	≥ 90 and increase from baseline ≥ 10
Pulse (bpm) (Supine or sitting)	< 50 and decrease from baseline ≥ 15	> 100 and increase from baseline ≥ 15

Abbreviations: BP = blood pressure; bpm = beats per minute.

